6.2 ACCESS TO BLINDED TREATMENT ASSIGNMENT

In the event of a medical emergency that requires immediate unblinding, an unblinding call may be made to determine treatment assignment. The identity of a subject's treatment assignment, should it need to be obtained, will occur through an unblinding call to the 24 hour [REDACTED]

[REDACTED]. Investigators will be permitted to access the treatment assignment upon the subject meeting the criterion for clinical worsening or after the completion of Day 14 if required for purposes of medically managing the subject (e.g., another prostacyclin will be initiated). Subjects randomized to placebo may be discontinued from study drug at that time. Subjects randomized to Remodulin who have residual or chronic pulmonary hypertension that does not fully resolve by Day 14 may continue to receive study drug for up to an additional 14 days (for a total of up to 28 days) per the Investigator's discretion. Subjects who have PPHN resolved by Day 14, who have already begun weaning by Day 14 or for whom it is anticipated that weaning of study drug will begin within

shortly after completing Day 14, or who are withdrawn from the study should remain blinded. All attempts should be made to maintain the blind during the study.

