- Post-treatment data will be collected until subject is withdrawn from the study, death, time of hospital discharge, or until 4 weeks after last dose of study drug, whichever comes first.
 - The following key assessments will occur at time of withdrawal from study, hospital discharge, or at 4 weeks after last dose of study drug, whichever comes first: physical exam, vital signs, and clinical laboratory assessments.
 - Additionally, time on mechanical ventilation, time on inhaled iNO, and time of initiation of EMCO (if applicable) will be recorded.
 - The subject's participation in the study will conclude at the time of hospital discharge, death, withdrawal from the study, or at 4 weeks after last dose of study drug, whichever comes first.
 - Subjects with ongoing AEs at the time of study withdrawal or hospital discharge will continue to be followed for their AEs until either resolution (or return to normal or Baseline values), until judged by the Investigator to no longer be clinically significant, or until 4 weeks after last dose of study drug. All SAEs will be followed until resolution, death, or the subject is lost to follow-up, even if they are ongoing more than 4 weeks after the last dose of study drug.

Statistical Considerations	Based on the systematic review of use of nitric oxide for respiratory failure in infants by Finer and Barrington, 57.9% (194/335) subjects in the control group had an outcome of death or requirement for EMCO. In this study, assuming 60% subjects in placebo group and 30% subjects in Remodulin group with an outcome of death, requirement for EMCO, or need for additional PAH therapy, we calculated that 66 subjects (33 subjects per treatment group) will have at least 80% power to show a significant difference in favor of Remodulin at alpha level of 0.05 (one-sided test).
-----------------------------------	--

Approximately seventy subjects are planned to be randomized (1:1) to either receive treatment with Remodulin or placebo on top of the standard of care.

Sponsor United Therapeutics Corp.
 [name]
 [name]
 [name]

TABLE OF CONTENTS

LIST OF CONTACTS FOR STUDY	2
INVESTIGATOR'S AGREEMENT	3
PROTOCOL SYNOPSIS	4
TABLE OF CONTENTS.....	10
Table of In-text Tables.....	14
Table of In-text Figures	14
LIST OF ABBREVIATIONS	15
1 BACKGROUND AND RATIONALE	17
1.1 DEFINITION OF CLINICAL PROBLEM.....	17
1.2 REMODULIN (TREPROSTINIL) BACKGROUND	18

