3 EXPERIMENTAL PLAN**3.1 STUDY DESIGN**

This is a randomized, double-blind, placebo-controlled, multi-center, comparative study that will enroll neonates in the intensive care unit (ICU) with PPHN. Eligible subjects must have two consecutive OIs of 15 or greater, separated by at least 30 minutes, after having received iNO for at least 3 hours. Once enrolled, subjects will be randomized to receive Remodulin (treprostinil) or placebo.

This study is designed to evaluate the treatment effect of Remodulin as add-on therapy compared to placebo during a 14-day treatment period. However, to assess continued safety in this neonatal population, subjects with residual or chronic pulmonary hypertension that does not fully resolve within 14 days may continue to receive study drug for up to an additional 14 days (up to 28 days total) per the Investigator's discretion. Post-treatment data will be collected until death, time of hospital discharge, time of withdrawal from study, or for 4 weeks after last dose of study drug, whichever comes first. Subjects with ongoing AEs at the time of hospital discharge will continue to be followed for their AEs until either resolution (or return to normal or Baseline values), until judged by the Investigator to no longer be clinically significant, or until 4 weeks after last dose of study drug. All SAEs should be followed until resolution, death, or the subject is lost to follow-up, even if they are ongoing more than 4 weeks after last dose of study drug.

Figure 3-1 Design Schematic

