3.6 ESTIMATED STUDY DURATION

No subject will receive study drug for greater than 28 days (4 weeks). Post-treatment data will be collected until death, time of hospital discharge, time of study withdrawal, or until 4 weeks after last dose of study drug, whichever comes first. Subjects with ongoing AEs at the time of hospital discharge or study withdrawal will be followed for their AEs until either resolution (or return to normal or Baseline values), until judged by the Investigator to no longer be clinically significant, or for up to 4 weeks beyond the subject's last dose of study drug. Therefore, the maximum amount of time a subject randomized to study drug would be in the study is 56 days (a maximum of 28 days of study drug, plus 4 week follow-up (28 days) after last dose/discontinuing study drug). Per the Investigator's discretion, if Remodulin treatment is needed beyond Day 28, subjects will be transitioned to commercial product; Day 28 will be considered as the last day of study drug administration. These subjects will continue to be followed in the study until they have reached Day 56 (4 weeks after last dose of study drug), have been discharged from the hospital or withdrawn from the study, whichever comes first.

The study will be completed once 66 evaluable subjects have been enrolled and completed the last patient last visit/assessment.

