4.3 PRESCRIBED THERAPY

4.3.1 *Concomitant Medications*

All subjects will be concurrently receiving iNO prior to randomization. Subjects should be adequately treated (as determined by the Investigator) with standard of care treatments for PPHN (e.g., inotropes, opioids, sedation) prior to enrollment and during the study. Doses of medications should be adjusted as needed during the study. All concomitant medications will be recorded in the subject's eCRF up until 48 hours after discontinuation of study drug. Any concomitant medications used in the treatment of an AE or SAE will be recorded even if it occurs more than 48 hours after discontinuation of study drug.

Caution should be used with cytochrome P450 (CYP) 2C8 enzyme inducers/inhibitors, such as rifampin or gemfibrozil, as plasma concentrations of treprostinil may be altered. Concomitant administration of Remodulin with diuretics, antihypertensive agents or other vasodilators may increase the risk of symptomatic hypotension. Remodulin inhibits platelet aggregation, there may be an increased risk of bleeding when administered with other anticoagulants, such as warfarin, heparin, or NSAIDs.

4.3.1.1 *Inotropic Dose Changes*

Doses of inotropic and vasoactive agents (e.g., dopamine, epinephrine, dobutamine, milrinone, vasopressin, norepinephrine) will be recorded with each dose change of study drug.

4.3.1.2 *Initiation of a Pulmonary Vasodilator Therapy*

If the Investigator initiates a targeted pulmonary vasodilator (after meeting the requirements outlined in Section 3.3.1.1.1) during the first 14 days after randomization, the subject will meet the definition of the primary endpoint of clinical worsening.

Subjects randomized to study drug who meet the definition of clinical worsening may continue to receive study drug for a total of up to 28 days at the discretion of the Investigator.

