9.3 PERIOD OF OBSERVATION

For the purposes of this study, the period of observation starts from the time the informed consent is signed and concludes upon meeting screen failure criteria, at the time of death, at the time of hospital discharge, at the time of withdrawal from the study, or at 4 weeks after last dose of study drug, whichever comes first. Day 28 will be considered as the last day of study drug administration for subjects who continue on Remodulin. Subjects with ongoing AEs at the time of hospital discharge will continue to be followed for their AEs until either resolution (or return to normal or Baseline values), until judged by the Investigator to no longer be clinically significant, or until 4 weeks after last dose of study drug. All SAEs should be followed until resolution, death, or the subject is lost to follow-up, even if they are ongoing more than 4 weeks after the last dose of study drug.

If the subject receives commercial Remodulin after hospital discharge, beyond Day 56/End of study, or following withdrawal from the study, AEs/SAEs will be subject to AE/SAE reporting under local government post-marketing AE/SAE reporting requirements.

Supplemental measurements and/or evaluations may be necessary to investigate fully the nature and/or causality of an AE or SAE. This may include additional laboratory tests, diagnostic procedures, or consultation with other healthcare professionals. The eCRF pages should be updated with any new or additional information as appropriate.

If the Investigator detects an SAE in the study subject after the end of the period of observation, and considers the event possibly related to prior study treatment, he or she should contact the Sponsor to determine how the event should be documented and reported.

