10.2.8 Time on Mechanical Ventilation

A listing that includes start date and time, stop date and time, and total time on mechanical ventilation will be prepared. Time on mechanical ventilation will be summarized by treatment group, as appropriate. A Wilcoxon rank sum test will be conducted to assess differences between treatment groups.

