12.2 ADVERSE EVENTS

All AEs will be coded to PT and SOC using the latest version of the MedDRA coding dictionary. Treatment-emergent adverse events (TEAEs) are those AEs with onset date equal to or after the start date of the study drug. TEAEs will appear in listings and summaries. Non-treatment-emergent AEs (the AEs occurring after signing the Informed Consent Form (ICF), but before receiving study drug) will be listed, but will not be included in summary tables.

The AE listings will include the AE verbatim term and its corresponding PT and SOC, all eCRF details, and a treatment-emergent indicator flag. The following AE listings will be provided:

- All AEs
- Deaths
- SAEs
- AEs leading to permanent discontinuation of study drug

All AE summaries will be sorted by overall frequency and/or SOC and will include the number and percentage of subjects experiencing each type of AE, the total number of each type of AE, and the AE rate of each type of AE. AE rate will be calculated as the total number of AEs divided by the total patient days of exposure to study drug per treatment group.

The following AE summaries will be provided:

- AEs by SOC and PT
- AEs by PT
- Deaths
- SAEs by SOC and PT
- Non-serious AEs by SOC and PT
- AEs probably or possibly related to study drug by SOC and PT
- AEs leading to permanent discontinuation by PT
- AEs by SOC, PT, and severity (mild, moderate, severe)

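### Deaths, AEs, SAEs and ventilation time are recorded until 4 weeks after the last dose, which can differ by arm once an infant is unblinded, and the SAP sets no common end day

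*Protocol*

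**What the plan says.** **End of observation.** Protocol 3.6: "Post-treatment data will be collected until death, time of hospital discharge, time of study withdrawal, or until 4 weeks after last dose". Protocol 3.1 has the same rule, and Protocol 9.3 closes the AE observation period on it: "at the time of withdrawal from the study, or at 4 weeks after last dose of study drug, whichever comes first". The clock runs from the last dose, not from randomization. Protocol 3.6 gives 56 days as the maximum time in the study.

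**Last dose.** Protocol 6.2 lets the investigator learn the assignment at clinical worsening or after Day 14, where medical management requires it. Of placebo infants it then says: "Subjects randomized to placebo may be discontinued from study drug at that time". Remodulin infants whose pulmonary hypertension has not resolved by Day 14 may go on to Day 28. Under Protocol 4.3.1.2, infants who worsen "may continue to receive study drug for a total of up to 28 days at the discretion of the Investigator".

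**Analysis.** SAP 12.2: "Treatment-emergent adverse events (TEAEs) are those AEs with onset date equal to or after the start date of the study drug". That gives a start but no end. AEs are reported as numbers and percentages of infants, as event totals, and as events divided by patient-days of exposure. Ventilation time is collected in follow-up (Protocol synopsis: "Additionally, time on mechanical ventilation, time on inhaled iNO, and time of initiation of EMCO (if applicable) will be recorded"). SAP 10.2.8 says "Time on mechanical ventilation will be summarized by treatment group, as appropriate", followed by a Wilcoxon rank sum test. It gives no end day and no rule for death or discharge.

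By contrast, the primary endpoint and the three time-to-event endpoints in SAP Table 8-1 all stop at Day 14.

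**The concern.** If the length of observation depends on when study drug stops, and stopping can depend on the arm, then a percentage of infants with an event is a percentage over different lengths of time. Two infants with the same course and the same true risk can contribute differently to the death, SAE and AE tables, and to total ventilator days, only because one was found to be on placebo and stopped.

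The infants concerned have worsened or still have pulmonary hypertension at Day 14, so they are plausibly the ones most likely to have late events. Safety is part of the primary objective (Protocol 2.1). With about 33 infants per arm, one or two deaths visibly change a table.

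**Working it through.** **1. Reproduce the plan's figure.** Latest end of observation = last dose day + 28. With last dose on Day 28, 28 + 28 = Day 56, which matches Protocol 3.6.

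**2. Other stopping days, same formula.**

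| Last dose (day) | Latest end of observation (day) | 56 / that end |
|---|---|---|
| 2 | 30 | 1.87 |
| 7 | 35 | 1.60 |
| 14 | 42 | 1.33 |
| 28 | 56 | 1.00 |

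Among unblinded infants the gap can therefore be 56 − 42 = 14 days to 56 − 30 = 26 days, longer on drug. These are maxima: death, discharge or withdrawal ends observation sooner.

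**3. What the extra days could hold.** The documents give no late event rate, so I assume an equal constant hazard h of 0.001 to 0.004 per day in both arms.
- 26 days: 1 − exp(−26h) = 2.6% to 9.9%.
- 14 days: 1 − exp(−14h) = 1.4% to 5.4%.

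These apply only to infants alive, in hospital and in the study when the shorter window closes. As events: the planning assumption gives 0.30 × 33 ≈ 10 worsened Remodulin infants. If all 10 were treated to Day 28 and remained at risk, 10 × 2.6% to 10 × 9.9% is about 0.3 to 1.0 event recorded after Day 30. None would be recorded in matching placebo infants stopped at Day 2.

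**4. Net effect across whole arms.** Inputs: worsening of 60% on placebo and 30% on Remodulin (Protocol 10.2). Assumptions: a share f of worsened placebo infants is stopped on day t (2 to 7), all other worsened infants in both arms continue to Day 28, non-worsened infants have their last dose on day x (7 to 14), and death and discharge are ignored.

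Placebo mean = 0.6 × [f(t + 28) + (1 − f) × 56] + 0.4 × (x + 28)

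Remodulin mean = 0.3 × 56 + 0.7 × (x + 28)

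- f = 1, t = 2, x = 14: placebo 0.6 × 30 + 0.4 × 42 = 34.8; Remodulin 16.8 + 29.4 = 46.2; ratio 1.33.
- f = 0, x = 7: placebo 33.6 + 14.0 = 47.6; Remodulin 16.8 + 24.5 = 41.3; ratio 0.87.

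Over the ranges of t and x, the ratio of Remodulin to placebo is 1.18 to 1.33 at f = 1, 1.00 to 1.08 at f = 0.5, and 0.87 to 0.92 at f = 0. It can fall on either side of 1.

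**5. Does the AE rate repair this?** Events are counted over up to L + 28 days but divided by L exposure days, where L is the last dose day. For a constant true daily rate and full follow-up, the inflation is (L + 28)/L: 15.0 at L = 2, 3.0 at L = 14 and 2.0 at L = 28. The rate is inflated most for infants stopped early. It does not correct the percentages and can be distorted in the opposite direction.

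**6. Is Day 28 already covered?** The last dose is on Day 1 or later, so observation runs to at least Day 1 + 28 = Day 29, unless the infant dies, is discharged or is withdrawn.

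**The case against.** Much can be said against a stronger reading of this point.

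- *A reader might infer that the drug is made to look worse.* The documents do not support that as a net effect. Protocol 6.1.1 defines study drug as Remodulin or placebo, so a placebo infant who stays blinded may also be treated to Day 28 and observed to Day 56. If few placebo infants are stopped, the longer mean window can be on placebo.
- *A reader might infer that about 20 of 33 placebo infants (60%) are stopped early.* That is an upper bound. Protocol 6.2 ties unblinding to medical need and asks that the blind be kept. Protocol 6.1.5 says that ECMO alone is not a reason to unblind. Infants who die have no later window. The number unblinded and stopped is not given.
- *A reader might infer that the primary endpoint is biased by this route.* An infant unblinded for worsening already has the event, and after Day 14 the endpoint is closed. (One sentence in Protocol 3.3.1.1 also ends assessment at discontinuation of study drug. It needs reconciling with Protocol 10.3.1, but that is a separate matter.)
- SAEs that have begun are followed to resolution or death, even beyond 4 weeks, so a death from an SAE that began inside the window can be captured in either arm. The gap concerns new late events. Under Protocol 9.3, a new SAE after the observation period leads to contact with the sponsor only if it is thought possibly related.
- Safety summaries are descriptive (Protocol 10.3.3). The ventilation test is exploratory and is run only if the primary is significant (SAP 8.4).

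All of this limits size, direction and consequence. None of it supplies a common end day, and descriptive tables will still be read as comparisons between arms.

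**Conclusion.** The point holds in a limited form. In infants unblinded at clinical worsening or after Day 14, the maximum observation window can differ by arm, for example Day 30 or Day 42 on placebo against Day 56 on Remodulin. The SAP sets no common end day for the death, SAE and AE percentages or for ventilation time, so these comparisons can be biased.

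Within unblinded infants with unresolved disease, the longer window is on drug. Across whole arms, neither direction nor size can be stated. The mean-window ratio of 0.87 to 1.33 rests on assumed stopping patterns, and the 0.3 to 1.0 event rests on assumed hazards and on every worsened Remodulin infant being treated to Day 28 and remaining at risk. Confidence is moderate: the mechanism is in the text, but its extent depends on how many infants are unblinded and stopped.

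**What to change.** 1. **SAP 12.2.** Add between-arm tables of deaths, SAEs and AEs (number and percentage of infants) from first dose to Day 28 regardless of last dose, with the number still under observation in each arm. That number is needed because a fixed day does not remove differences in discharge timing.
2. **Keep the full-window tables** as separate output, including events after Day 28 and after study drug is stopped.
3. **SAP 10.2.8.** Compare ventilation time to Day 28 with a stated rule for death and discharge, for example ventilator-free days to Day 28 with death scored as zero. Without such a rule, an early death counts as short ventilation.

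The changes should be made before unblinding of the database. The cost is SAP wording, a date filter and a few extra tables, with no new data collection and no change to dosing or unblinding. The downside is that the Day 28 table holds little off-drug time for infants treated to Day 28, which is why the full-window tables should stay beside it.

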6.3 COMPLIANCE

The study will occur within the intensive care unit. All dosing will be administered by qualified medical personnel. Accurate pharmacy and clinical records will be maintained to ensure appropriate doses and dose adjustments are made.

7 EXPERIMENTAL PROCEDURES

7.1 SCREENING

Screening will occur once written informed consent has been obtained from the parent(s) or legal guardian(s). Some Screening and Baseline assessments may be combined if conducted within 3 hours of randomization (noted with “*” below).

Screening activities will include the following:

- Informed consent
- Confirmation of inclusion/exclusion criteria
- Maternal and child history
 - Including birth weight, and the one and five-minute Apgar score
- Physical examination*
- Vital signs (BP, HR, Temp, pre and post-ductal SpO₂)*
- OI assessment*
- Record FiO₂ and MAP (including type of ventilation – high frequency vs. traditional)*
- Arterial blood gas*
- Echocardiogram
- Record concomitant medications
- Record any AEs once informed consent has been provided

7.2 BASELINE

Once all Screening activities have taken place, the following Baseline activities will occur. Once Baseline assessments have been completed and eligibility confirmed, subjects may be randomized in the IWRS. Study drug should be initiated as soon as possible after randomization.

- Physical examination (including length and weight)*
- Vital signs (BP, HR, Temp, pre- and post-ductal SpO₂)*
- OI assessment*

- Record FiO₂ and MAP (including type of ventilation – high frequency vs. traditional)*
- Arterial blood gas*
- Clinical laboratory assessments (See Section 3.3.2.3)
- NT-proBNP
- Randomization
- Initiation of study drug
- Assess clinical worsening
- Record concomitant medications
- Record any AEs

Some Screening and Baseline assessments may be combined (i.e., not repeated) if conducted within 3 hours of randomization (noted with “*”).

7.3 TREATMENT PHASE

7.3.1 *First 72 Hours*

The following assessments will be obtained during the first 72 hours of study drug administration.

- Physical examination (once daily)
- Vital signs approximately every 6 hours (BP, RR, HR, Temp, pre- and post-ductal SpO₂)
- OI assessment approximately every 6 hours (as long as the subject is on mechanical ventilation and ABGs are obtained)
- FiO₂; approximately every 6 hours
- MAP approximately every 6 hours (as long as the subject is on mechanical ventilation)
- Blood gases approximately every 6 hours (ABG if possible, otherwise CBGs/VBGs)
- NT-proBNP (once daily)
- Record concomitant medications
- Continue study drug, up-titrating as needed
 - BP, HR, and SpO₂ will also be collected with each study drug dose change
 - Record doses of inotropes with each study drug dose change
- Record AEs
- Collect PK sample 24 hours after the start of study drug dosing. Sample should be collected at least 2 hours after the last dose change (See Section 3.3.3 and Appendix 15.2)
- Assess clinical worsening (throughout the 14 day study period)

7.3.2 *Study Day 4 Throughout Duration of Study Drug Therapy*

The following assessments will be obtained daily starting on the fourth day of study drug administration and continue throughout the duration of study drug therapy:

- Vital signs (BP, RR, HR, Temp, SpO₂)
- OI assessment (as long as the subject is on mechanical ventilation and ABGs are obtained)

- FiO₂
- MAP (as long as the subject is on mechanical ventilation)
- Blood gases (ABG if possible, otherwise CBGs/VBGs)
- Record concomitant medications
- Continue study drug, up-titrating as needed
 - BP, HR, and SpO₂ will also be collected with each study drug dose change
 - Record doses of inotropes with each study drug dose change
- Record AEs
- Assess clinical worsening (throughout the 14 day period)

Subjects who have residual or chronic pulmonary hypertension that does not fully resolve by Day 14 may continue to receive study drug for up to an additional 14 days (for a total of up to 28 days) per the Investigator's discretion.

7.3.2.1 Study Day 7 and Day 14

The following assessments should be performed on study Day 7 and Day 14 regardless if the subject has already been weaned from study drug. If the subject will be discharged from the hospital prior to Day 14, the Day 14 assessments should be completed prior to hospital discharge.

- Physical examination
- Vital signs (BP, RR, HR, Temp, SpO₂)
- OI assessment (as long as the subject is on mechanical ventilation and ABGs are obtained)
- FiO₂
- MAP (as long as the subject is on mechanical ventilation)
- Blood gases (ABG if possible, otherwise CBGs/VBGs)
- Clinical laboratory assessments (See Section 3.3.2.3)
- NT-proBNP
- Echocardiogram
- Record concomitant medications
- Continue study drug, up-titrating as needed
 - BP, HR, and SpO₂ will also be collected with each study drug dose change
 - Record doses of inotropes with each study drug dose change
- Record AEs
- Assess clinical worsening (throughout the 14-day period)

